For those centers in whom laboratory thrombophilia testing is performed as part of routine clinical care in the target population, this will have been performed clinically by the time of enrollment; those centers in whom laboratory thrombophilia testing is not considered to be part of standard/best clinical care will perform this testing on patients who have provided informed consent for study participation and are undergoing screening procedures for the study.

The overall study schema, with regard to enrollment, randomization (versus observational parallel cohort assignment), and long-term follow-up, is shown below (Figure 1).

The study Schedule of Events is shown below (Table 2), followed by a more detailed description of the procedures and components that comprise each visit in Section E. All visits are timed from the date of radiologic diagnosis.

Table 2. Schedule of Events

Assessment Performed	Screening	Clinic Follow-up Visit 2	Telephone Follow-up Visit 3	Clinic Follow-up Visit 4	Clinic Follow-up Visit 7 ^a **	Clinic Follow-up Visit 8**	Clinic Follow-up Visit 9**
	Within 30 days diagnosis	6 weeks +/- 7 days post-diagnosis	8 weeks +/- 7 days post-diagnosis	12 weeks +/- 10 days post-diagnosis	6 months +/- 14 days post-diagnosis	1 year +/- 30 days post-diagnosis	2 years +/- 30 days post-diagnosis
Informed consent	X						
Enrollment	X [#]						
Full medical history	X	X		X	X	X	X
Physical exam	X	X		X	X	X	X
Height & Weight	X						
Thrombophilia Testing	X ^a	X ^c					
Research Blood		X ^b		X ^b			
Telephone questionnaire ^d			X		X**	X**	X**
Patient Diary and Anticoagulant Calendar Review		X	X	X			
Web-based data collection	X	X	X	X	X	X	X
Recurrent VTE history		X	X	X	X	X	X
Bleeding history		X	X	X	X	X	X
PTS evaluation [^]					X%	X%	X%
AEs assessment (for randomized participants only)		X	X	X			
Randomization		X [#]					

^a Protein C; Protein S; Antithrombin; APA Testing:

Anticardiolipin Antibody (ACA) IgM, Beta-2 Glycoprotein IgG, Beta-2 Glycoprotein IgM; Lupus Anticoagulant (LAC) – only one of the following is required:

dRVVT, aPTT-based Hexagonal Phospholipid, or aPTT-based Non-hexagonal Phospholipid. Anticoagulant monitoring as appropriate, if not yet documented within the goal therapeutic range

^b Research blood for CloFAL assay, plasma proteomics is required for all participants. Research Blood for DNA/RNA only collected for those participants who consent to genetic material. (See Lab Manual for details)

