
Visit 1 – Within 30 days of radiologic diagnosis:

- Informed consent
- Full medical history and physical exam
- Thrombophilia testing:
 - Protein C level (activity preferred)
 - Protein S level (free protein S antigen preferred)
 - Antithrombin (III) level (activity preferred)
 - APAs (including lupus anticoagulant):
 - Anti-cardiolipin IgM
 - Beta-2 glycoprotein IgG
 - Beta-2 glycoprotein IgM
 - Lupus anticoagulant – testing paradigm must include both a mixing study and a phospholipid neutralization step, as per ISTH guidelines for lupus anticoagulant testing (note: if both steps are included in a single test, then that single test will suffice for lupus anticoagulant testing):
 - dilute Russell Viper Venom Time (dRVVT), AND/OR
 - aPTT-based Hexagonal Phospholipid (e.g., STA-Clot), AND/OR
 - aPTT-based Non-hexagonal Phospholipid (e.g., lupus-sensitive aPTT)

Visit 2 – 6 weeks (+7/-5 days) post-diagnosis:

- Full medical history* and physical exam
- Research blood collection (Please refer to laboratory manual for details)
- Repeat imaging, using the same imaging modality as was used for thrombosis diagnosis. This is part of best/standard clinical care at participating centers. Note: Repeat imaging at 6 weeks is not required if interim imaging was already performed clinically and showed complete resolution of thrombosis.
- Repeat testing of any APA tests that were positive at enrollment (see Visit 1 for details). As described above for thrombophilia testing at enrollment, this repeat APA testing is performed as part of best/standard clinical care at many but not all participating centers. Note: Positive APA is defined as any of the following or combination thereof:
 - Anticardiolipin (IgM) >20 MPL U/mL
 - Beta-2 Glycoprotein (IgG) >20 GPL U/mL
 - Beta-2 Glycoprotein (IgM) >20 MPL U/mL
 - dRVVT abnormal/positive
 - aPTT-based, Hexagonal Phospholipid abnormal/positive
 - aPTT-based, Non-Hexagonal Phospholipid abnormal/positive
- Randomization vs. non-random assignment to an observational arm ("parallel cohort"; Goldenberg et al. 2010a)
 - Participants with evidence of complete resolution of deep venous thrombosis, residual non-occlusive thrombus in a non-distal deep venous system, or residual occlusive thrombus confined to a distal venous system (constituting the "thrombus resolution/non-proximal-

occlusion group"), AND who do not have persistent APA, will be randomized to receive one of two anticoagulant treatment durations:

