A participant who is still on anticoagulant treatment when she becomes pregnant, may be retained in the study on the allocated treatment duration arm so long as the primary hematologist believes that this is clinically appropriate; else she will be withdrawn from the study and treated with the clinically-indicated duration of anticoagulation.

Off-Study Criteria:

1. Participant not randomized within 8 weeks of radiologic diagnosis of qualifying VTE, despite meeting criteria for randomization.
2. In the investigator's opinion, it is in the participant's best interest to discontinue participation.
3. Study discontinuation by sponsor, IRB, or other regulatory body.
4. Lost to follow-up: Participants will not be deemed lost to follow-up until they have had no successful contact by the end of the 2 year visit window. Sites must document all attempts to contact the participant.
5. Participant stops anticoagulation prior to randomization and does not intend to continue further anticoagulation.

G. Potential Scientific Problems:

Although this study involves relatively minimal intervention, main potential problems and challenges include loss to follow-up/drop-out during the follow-up period, low endpoint rates, and the rather large projected number of patients required to achieve adequate power. These challenges were indeed observed during the pre-specified pilot/feasibility period of the study. The Steering Committee recommended strategies to overcome these challenges, and these recommendations were adopted and reflected via protocol modifications during the pilot/feasibility period and the transition from the vanguard phase to the NHLBI U01-funded phase of the trial.

Other challenges stem from the multi-center nature of the study, including uniformity of data collection and anticoagulant management, and timely data entry into the EDC system. These challenges are overcome via the CCC and DCC structure and close oversight of the trial, the use of EDC system with standardized eCRFs, and the agreement of all participating centers to follow established anticoagulant management guidelines (American College of Chest Physicians) for pediatric VTE treatment. During the pilot/feasibility period of the trial, these potential challenges did not materialize as substantive issues.

H. Data Analysis Plan:

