Recurrent VTE, bleeding events (major and clinically-relevant non-major), PTS, and death will be considered outcome events rather than adverse events.

Adjudication of outcome events:

Outcome events will be centrally adjudicated via an independent, blinded Clinical Endpoint Adjudication Committee (CEAC). Please see the Manual of Operations (MOO) for submission instructions.

2. Deviation Reporting Guidelines

A protocol deviation is defined as a variation from the protocol-directed conduct of a clinical trial. Any non-compliance with the study protocol, GCP, ICH guidelines, or a protocol-specific requirement is considered a protocol deviation. Protocol deviations will be entered into the EDC and reported to the site IRB per site policy.

Major Protocol Deviations

Major Protocol Deviations are defined as deviations that impact patient safety or the final outcome measures of the trial. Deviations that meet the defined criteria as Major Protocol Deviations will be reported within 5 days of identification of deviation to the CCC Project Manager and the site institutional review board (IRB) per local IRB policy.

Major Protocol Deviations include, but are not limited to:

1. Inappropriate enrollment; expired protocol*, violation of eligibility criteria or incomplete consent documentation*
2. Violation of any site specific IRB requirements (e.g. If sites IRB requires both parents to sign consent)
3. Randomization of patient outside randomization visit window (week 6) or other inappropriate randomization
4. Failure to report SAE in the 24 hour time period following knowledge of SAE*
5. Failure to provide source documentation of a primary efficacy or safety outcome, as well as death event, for central adjudication by the Clinical Endpoint Adjudication Committee (CEAC).

*items are identified as major protocol deviations, but do not disqualify participant's data to be included in the per protocol analysis.

Minor Protocol Deviations

Minor Protocol Deviations are defined as deviations that do not impact patient safety or the final outcome measure of the trial, but do not follow study specified guidelines. All deviations that are not determined to be major deviations are to be recorded as minor deviations.

Minor Protocol Deviations include, but are not limited to:

1. Missed visits or visits outside study windows (except missed/out-of-window for week 6 visit, which constitutes a MAJOR Deviation)

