2. ANALYSIS PLAN

2.1. Primary analysis

2.1.1 Definition of analysis populations

The primary analysis will be based on the per-protocol (PP) analysis for the primary endpoint. The companion intent-to-treat (ITT) analysis will also be completed and reasons for disagreement will be evaluated. A “positive” trial is one in which the primary hypothesis is true for both the PP and ITT analyses.

- ITT: All randomized patients (i.e., excluding those in the parallel cohorts), analyzed according to randomization assignment.
- PP: All randomized patients (i.e., excluding those in the parallel cohorts) who satisfy all of the following conditions:
 - Completed follow-up through at least the 6 month visit (note that per-protocol, the 6 month visit and subsequent long-term follow-up visits may be conducted via phone).
 - Received 80-120% of doses of anticoagulant medication based on protocol-prescribed randomized duration of anticoagulation.
 - Had no protocol violations in eligibility criteria.

- c) Safety: All randomized patients who have received at least 1 dose of anticoagulant post-enrollment.

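### The protocol's deviation footnote implies per-protocol exclusions that neither PP definition contains, and one of them can apply only to a child with a reported endpoint event or death

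*Protocol*

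**What the plan says.** SAP 2.1.1 makes PP the primary analysis population and admits every randomized child who meets three conditions: follow-up to at least the 6-month visit, 80-120% of the doses prescribed for the allocated duration, and, in the SAP's words, "Had no protocol violations in eligibility criteria". Protocol IV.H gives the same three in substance. SAP 2.1.1 also calls the trial positive only if the hypothesis holds in both PP and ITT. SAP 2.1.2 measures effects on centrally adjudicated events.

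Protocol IV.J.2 lists major deviations. A footnote says that those with an asterisk "do not disqualify participant's data to be included in the per protocol analysis". The asterisk is on expired protocol and incomplete consent documentation (both in item 1) and on late SAE reporting (item 4). It is absent from:

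- item 2: "Violation of any site specific IRB requirements";
- item 3: "Randomization of patient outside randomization visit window (week 6) or other inappropriate randomization";
- item 5: "Failure to provide source documentation of a primary efficacy or safety outcome, as well as death event, for central adjudication".

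The window that item 3 relies on is given twice. Table 2 has Visit 2 at "6 weeks +/- 7 days post-diagnosis"; the Visit 2 description in IV.F has "6 weeks (+7/-5 days) post-diagnosis".

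**The concern.** If the footnote is read as a PP rule, the protocol removes children from the primary population for three reasons that its own analysis section and the SAP do not recognise. Two analysts working from the same documents could build different primary datasets.

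Item 5 matters most. A child with no reported endpoint event and no death cannot incur it, so excluding on it conditions the analysis set on the outcome. Such gaps are plausible: Protocol IV.F expects events seen away from the site to be verified from outside medical records. Treatment is open-label, so equal completeness of documents in the two arms cannot be taken for granted. With few events expected, a single exclusion could matter.

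**Working it through.** **1. Does the footnote imply exclusion?** A statement that marked items do not disqualify does nothing unless unmarked items can. Item 1 supports this reading. Its two administrative phrases carry asterisks, while the eligibility violation beside them does not, and that violation is an exclusion in both PP definitions. The asterisks appear to have been placed phrase by phrase to signal PP status.

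| Unasterisked deviation | In Protocol IV.H or SAP 2.1.1? |
|---|---|
| Eligibility violation (item 1) | Yes, both |
| Site IRB requirement (item 2) | No |
| Out-of-window or inappropriate randomization (item 3) | No |
| Missing documents for an endpoint event or death (item 5) | No |

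**2. Visit 2 window.** Six weeks is day 42. Table 2 gives 42 − 7 = 35 to 42 + 7 = 49. IV.F gives 42 − 5 = 37 to 49. They disagree on days 35-36 only.

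**3. The plan's own precision.** SAP Table 4 at 316 children, taken as 158 per arm (1:1 assumed), with half-width 1.96 × √(p(1 − p) × 2/158):

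- srVTE, p = 0.03: 0.0376 (SAP 0.038)
- bleeding, p = 0.01: 0.0219 (SAP 0.022)

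Both reproduce. Expected events in both arms together are 316 × 0.03 = 9.5 srVTE and 316 × 0.01 = 3.2 bleeds. One event is 1/158 = 0.63 points of an arm's risk.

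**4. Decision rule.** From SAP Appendix equation (2), S_arr = √(0.1 × 0.9 × 2/285) = 0.0251, so the curve has constants 0.025 + 1.96 × 0.0251 = 0.0743 (srVTE) and 0.08 + 1.96 × 0.0251 = 0.1293 (bleeding). Non-inferiority is met when both upper limits lie below their constants and (0.0743 − U_V)(0.1293 − U_B) exceeds 0.003.

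The upper limits are melded exact limits, as SAP 2.1.3 specifies: the 97.5th percentile of Beta(x_s + 1, n_s − x_s) minus an independent Beta(x_c, n_c − x_c + 1), where s is short and c is conventional.

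With assumed bleeds of 1 short v 2 conventional, U_B = 2.56%. The largest srVTE limit allowed is 0.0743 − 0.003/(0.1293 − 0.0256) = 4.53%, and this stays at 4.53% after any of the single exclusions below.

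**5. Effect of one exclusion (the excluded child has no bleed).**

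| srVTE short v conventional | Upper limit | PP non-inferiority |
|---|---|---|
| 5/158 v 5/158, event counted | 4.75% | not met |
| 4/157 v 5/158, short-arm child excluded | 3.94% | met |
| 4/158 v 5/158, child kept, event not counted | 3.90% | met |
| 4/158 v 4/158, event counted | 4.40% | met |
| 4/158 v 3/157, conventional-arm child excluded | 4.88% | not met |
| 4/158 v 3/158, child kept, event not counted | 4.89% | not met |

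The large shifts, 0.81 and 0.48 points, separate a counted event from an uncounted one. Excluding the child, once the event is uncounted, adds 3.94 − 3.90 = 0.04 points in the first case and changes the limit by 4.89 − 4.88 = 0.01 in the second.

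**The case against.** The strongest reply is that no sentence excludes these children. IV.J.2 tells sites what to report, while two concordant definitions fix the PP population. That stands as far as it goes: a reader might infer that the protocol states an exclusion rule, and it only implies one. But the implication is hard to avoid, because the footnote names the PP analysis and otherwise has no function.

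Second, only adjudicated events count. An event without documents may never be adjudicated, and then it is lost whether or not the child stays in PP. This also stands. A reader might infer from the 4.7% to 3.9% shift that the footnote by itself can decide the trial. It has that effect only if the committee would have confirmed the event on the documents it did hold. How such cases are handled is left to the adjudication charter and operations manual, which are not part of these documents.

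Third, ITT must also be positive, and item 5 cannot remove a child from ITT. This limits false non-inferiority. It does not help when a conventional-arm exclusion makes PP fail, nor when the unadjudicated event drops out of ITT as well.

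Two further readings go too far. Open-label sites might suggest a bias toward non-inferiority, but the documents report no item 5 deviations and no imbalance, and the effect can run either way. It is also tempting to call item 3 undefined up to day 56, because the off-study rule reads "Participant not randomized within 8 weeks of radiologic diagnosis of qualifying VTE". Days 50-56 are outside both windows and so are plainly a major deviation; an off-study limit can coexist with a narrower visit window.

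**Conclusion.** The conflict is real. The footnote implies PP exclusions under items 2, 3 and 5 that the closed three-condition definition does not contain, and item 5 would exclude children because an endpoint event or death was reported. Some deaths before 6 months may already fail the follow-up condition.

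The consequence is conditional. At 158 per arm with the assumed counts, excluding one child whose event would otherwise be counted can reverse the PP result in either direction. If the event would be uncounted anyway, the exclusion moves the limit by at most about 0.04 points in the cases shown. The counts are illustrative, chosen near the 9.5 srVTE and 3.2 bleeds expected at the SAP's 3% and 1% risks. The documents do not support a claim that the primary result is biased in a known direction, or that the footnote alone would settle it.

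**What to change.** Replace the IV.J.2 footnote with a statement that PP membership is governed solely by SAP 2.1.1 and that no deviation concerning event documentation excludes a participant.

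Have the blinded committee adjudicate on whatever documents are available, and keep adjudicated events as the primary count. Add a sensitivity analysis, in PP and in ITT, that counts site-reported events that could not be adjudicated. Counting those events in the primary analysis would bring unblinded site judgement into a design built on blinded assessment, so they belong in the sensitivity analysis.

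Reconcile the Visit 2 windows in Table 2 and IV.F so that days 35-36 have one status under item 3.

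The cost is a footnote, a short addition to the SAP and one extra sensitivity analysis, with no new data collection. The primary database was locked in March 2021 (Protocol IV.I), so the clarification should be dated and should state which PP rule was applied.

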Children's Hospital Colorado / University of Colorado	Aurora	CO	U.S.A.	[name]
UC Davis	Sacramento	CA	U.S.A.	[name]
University of Rochester Medical Center / University of Rochester	Rochester	NY	U.S.A.	[name], PhD
University of Virginia	Charlottesville	VA	U.S.A.	[name]

Appendix 2: Kids-DOTT Secondary Manuscripts Approved to date by the Publications Committee and Steering Committee

1. Complete veno-occlusion following an initial six weeks of anticoagulant therapy for first-episode provoked VTE and the risk of adverse outcomes (srVTE, PTS) in patients < 21 y.o.
(DCC: CPC Clinical Research)
2. Durability of Kids-DOTT RCT Primary Findings at 2 Year Follow-up
(DCCs: CPC Clinical Research and Johns Hopkins All Children's DCC for Pediatric Multicenter Studies)
3. Prevalence of Persistent APA and APS and associations with outcomes in patients <21 y.o. with first-episode acute provoked VTE
(DCCs: CPC Clinical Research and Johns Hopkins All Children's DCC for Pediatric Multicenter Studies)
4. Predictors of clinically-significant PTS in patients <21 y.o. with first-episode provoked VTE
(DCC: Johns Hopkins All Children's DCC for Pediatric Multicenter Studies)
5. Predictors of symptomatic recurrent VTE in patients <21 y.o. with first-episode provoked VTE
(DCC: Johns Hopkins All Children's DCC for Pediatric Multicenter Studies)
6. Predictors of clinically-relevant bleeding in patients <21 y.o. with first-episode provoked VTE
(DCC: Johns Hopkins All Children's DCC for Pediatric Multicenter Studies)
7. Clinical characteristics, anticoagulant therapy, outcomes, and prognostic factors in patients <21 y.o. with first-episode provoked CSVT
(DCC: Johns Hopkins All Children's DCC for Pediatric Multicenter Studies)
8. Clinical characteristics, anticoagulant therapy, outcomes, and prognostic factors in patients <21 y.o. with first-episode provoked splanchnic venous thrombosis
(DCC: Johns Hopkins All Children's DCC for Pediatric Multicenter Studies)
9. Clinical characteristics, anticoagulant therapy, outcomes, and prognostic factors in cancer patients <21 y.o. with first-episode provoked VTE during remission
(DCC: Johns Hopkins All Children's DCC for Pediatric Multicenter Studies)
10. Clinical characteristics, anticoagulant therapy, outcomes, and prognostic factors in patients <21 y.o. with first-episode provoked non-proximal PE with underlying DVT
(DCC: Johns Hopkins All Children's DCC for Pediatric Multicenter Studies)
11. Clinical characteristics, anticoagulant therapy, outcomes, and prognostic factors in patients <21 y.o. with first-episode provoked right atrial thrombosis
(DCC: Johns Hopkins All Children's DCC for Pediatric Multicenter Studies)
12. Clinical characteristics, anticoagulant therapy, outcomes, and prognostic factors in patients <21 y.o. with first-episode central venous catheter (CVC)-related DVT
(DCC: Johns Hopkins All Children's DCC for Pediatric Multicenter Studies)
13. Anticoagulant medication adherence in the treatment of provoked VTE in patients <21 y.o.: Characterization, associated factors, and VTE outcomes
(DCC: Johns Hopkins All Children's DCC for Pediatric Multicenter Studies)

Prospective Multi-Center Evaluation of the Duration of Therapy for
Thrombosis in Children
(the “Kids-DOTT” Trial)

Document Date: 9/10/2021

NCT - NCT00687882

Prospective Multi-Center Evaluation of the Duration of Therapy for
Thrombosis in Children
(the “Kids-DOTT” Trial)

Document Date: 7/11/2019

NCT - NCT00687882

Statistical Analysis Plan

Protocol Title: Kids-DOTT

Sponsor: National Institutes of Health

Version Number: 2.00

Version Date: 11 July 2019

Prepared by: [name], Lead Trial Statistician

On Behalf of the Kids-DOTT Data Coordinating Center

CPC Clinical Research and University of Colorado

APPROVALS

Author

L

[name] PhD

W,
Date

CPC Approval

L

[name]

15
Date

Sponsor Approval

L

[name] MD

11: 1tvv 1-01
Date

Committee Approval

[name]

11
Date

TABLE OF CONTENTS

APPROVALS	2
TABLE OF CONTENTS	3
1. OVERVIEW OF STATISTICAL DESIGN FOR THE KIDS-DOTT RANDOMIZED TRIAL	4
1.1 Design overview	4
1.2 Statistical decision criteria using the bivariate (recurrent VTE:bleeding) outcome	5
1.2.1 Decision criteria for ARR in recurrent VTE and bleeding endpoints	5
1.3 Bivariate non-inferiority bound and trial power	6
1.3.1 Bivariate null hypothesis	7
1.3.2 Trial power	8
2. ANALYSIS PLAN	9
2.1. Primary analysis	9
2.1.1 Definition of analysis populations	9
2.1.2 Definition of endpoints	10
2.1.3 Analysis methods for primary endpoints	10
2.2. Secondary analyses	10
2.2.1 Secondary endpoints	10
2.2.2 Analysis methods for secondary endpoints	11
2.2.3 Missing data	11
2.3 Analysis of tertiary and exploratory endpoints	11
2.3.1 Analysis of subgroups	11
3. APPENDIX: BIVARIATE DECISION CRITERIA	12
REFERENCES	13

Kids-DOTT Randomized Trial Cohort Statistical Analysis Plan

The Kids-DOTT trial has two components: (1) a randomized controlled trial using a prospective randomized open-label blinded-endpoint (PROBE) design, wherein treatment is not blinded but outcome assessment is blinded, and (2) a parallel cohort comprised of children who are not eligible for randomization to short duration anticoagulation at the 6-week visit due to complete veno-occlusion or persistently positive antiphospholipid antibodies. The purpose of this statistical analysis plan is to describe the statistical analysis for the randomized controlled trial population. The analysis plan for the non-randomized parallel cohorts will be described in a separate document.

